#### 3.2.2. Secondary Study Endpoints

Secondary endpoints include:

- All-cause mortality at 30- and 60-days following last FMT
- Colectomy or diverting ileostomy within 30 days after last FMT
- Cumulative days of hospitalization from enrollment until 30 days after FMT
- Cumulative days in intensive care unit from enrollment until 30 days after last FMT
- Bacteremia from enrollment until 30 days after last FMT
- Repeat hospital admission within 60 days of discharge from index hospitalization

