#### **3.1.4. Post-PMT Administration monitoring: Daily for 3 Days after Administration/Enrollment**

The subject will be monitored every calendar day for three days after each PMT administration in order to assess their eligibility for repeat up to 2 additional doses of PMT at 3 days after the first administration and 3 days after a second administration (if given), as well as to assess for adverse events. If the subject continues to meet criteria for severe or severe-complicated disease within the prior 24 hours at 3 days after the initial administration and then 3 days after the second administration (if given), the subject will be eligible for a repeat dose of PMT (same formulation as per initial randomization). If PMT administration is unable to be performed at 3 or 6 days following the first administration, then administration within 1 calendar day before or after those days will be permitted. Assessment for eligibility for an additional dose will be performed on the day of repeat administration. For subjects in the non-PMT arm, monitoring will be performed daily for three days after enrollment for adverse event assessment.

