#### **3.1.5. Post-PMT Administration Follow-Up**

Following a subject's final PMT administration or enrollment for those in the non-PMT arm, subjects enter the follow up phase. During this phase, the following will occur: (1) while remaining inpatient, daily maximum temperature, number of bowel movements, and any episodes of emesis will be recorded (based on electronic medical record) for 7 calendar days post-FMT or post-enrollment for the non-PMT arm; (2) in preparation for discharge from the hospital, subjects will record daily temperature, number of bowel movements, and any episodes of emesis for 7 days post last FMT/post-enrollment (subjects will be given a symptom diary card; a digital thermometer will also be provided); (3) subjects will be contacted by telephone or in-person for an interview focused on potential adverse events at 7 days (or next working day, not to exceed 10 days) after final FMT or after enrollment for non-PMT arm; (4) subjects will be contacted by telephone or in-person at 30 days (+/- 3 days) after final FMT or after enrollment for non-PMT arm for an interview focused on potential adverse events; (5) subjects will be contacted by telephone or in-person at 90 days (+/- 7 days) after final FMT or after enrollment for non-PMT arm for an interview focused on potential adverse events; (6) subjects will be contacted by telephone or in-person at 180 days (+/- 7 days) after final FMT or after enrollment for non-PMT arm for an interview focused on potential adverse events.

Telephone versus in-person follow-up will be determined based on subject preference. (If subjects prefer to be seen in person, but have been discharged from the hospital, a clinic visit with a study team member will be arranged). All FMT recipients (or their surrogates) will be given contact information for the study coordinator. As detailed above, subjects will be followed for 180 days following last investigational product administration or after enrollment for non-PMT arm. All subjects will be also provided a study contact telephone number on a copy of the

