**6.5. Unscheduled Visits**

Data collected from subjects who contact the study team (by telephone, electronically, or in-person) outside of the scheduled visits (as above) will be associated with the next scheduled study visit, as each study visit is intended to retrospectively cover the time period since the last study visit.

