**Table 3: Schedule of study procedures**

Study Phase	Screening & Enrollment	Intervention	Follow-Up: 30 & 60 minutes	Follow-Up: First 3 Days	Follow-Up: 7 days	Follow-Up: 30 days	Follow-Up: 90 days	Follow-Up: 180 days
Study Days	1	1* (Retreatment Day 4 / 7*)	1* (Retreatment Day 4 / 7*)	Final Intervention +1, +2, +3	Final Intervention +7	Final Intervention +30	Final Intervention +90	Final Intervention +180
Surveillance Test Review	X							
Medical Record Review	X			X	X	X	X	X
Review Inclusion/Exclusion	X							
Informed Consent	X							
Enteral Access Check	X							
Randomization	X							
Dispense PMT to Clinical Site		X						
PMT Receipt Check		X						
PMT Administration		X						
Compliance Check		X						
Vital Signs Review			X	X	X			
Symptom Review			X	X	X	X	X	X
Laboratory Review				X	X	X	X	X
CRF3 / Outcomes Check				X	X	X	X	X
Adverse Event Check		X	X	X	X	X	X	X
Microbiome Swab from Otherwise Discarded Stool				X	X			
Immune Phenotypic Analysis on Otherwise Discarded Whole Blood				X	X			

\*If PMT administration is unable to be performed on days 1, 4 and/or 7, administration and 30/60-minute follow up within 1 calendar day before or after those days will be permitted (for the first administration, administration within 1 calendar day after enrollment will be permitted). If the first administration occurs on day 2, then the second and third administration dates (if eligible) will be days 5 and 8 (+/- 1 calendar day).

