### **8.2. Secondary Endpoints**

Secondary endpoints are detailed in [Section 3.2.2](#). Secondary endpoints will include all-cause mortality (30- and 60-days following enrollment), colectomy or diverting ileostomy within 30 days after enrollment, cumulative days of hospitalization from enrollment until 30 days after enrollment, cumulative days in intensive care unit from enrollment until 30 days after enrollment, bacteremia from enrollment until 30 days after enrollment, readmission within 60 days of discharge from index hospitalization.

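### Five of the six secondary endpoints have conflicting windows: Section 3.2.2 counts from FMT, Section 8.2 from enrollment, and the 3.2.2 version leaves controls without an anchor

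*Combined protocol and SAP*

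**What the plan says.** Section 3.2.2 lists six secondary endpoints. Mortality is "All-cause mortality at 30- and 60-days following last FMT", and colectomy or diverting ileostomy is likewise counted for 30 days from the last FMT. Three endpoints start at enrollment but end relative to a dose: "Cumulative days of hospitalization from enrollment until 30 days after FMT", "Cumulative days in intensive care unit from enrollment until 30 days after last FMT", and bacteremia, which ends as ICU days do. The sixth, readmission, runs 60 days from index discharge.

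Section 8.2 says the secondary endpoints are detailed in Section 3.2.2, then restates them differently: "Secondary endpoints will include all-cause mortality (30- and 60-days following enrollment), colectomy or diverting ileostomy within 30 days after enrollment". It also closes hospital days, ICU days and bacteremia 30 days after enrollment. Only readmission is the same in both places.

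The date of the last FMT depends on how the subject does after randomization. Section 3.1.4 makes a subject eligible for another dose "If the subject continues to meet criteria for severe or severe-complicated disease within the prior 24 hours" at the decision points. For follow-up contacts, Section 3.1.5 does give controls a substitute anchor: "subjects will be contacted by telephone or in-person at 30 days (+/- 3 days) after final FMT or after enrollment for non-PMT arm". Section 3.2.2 has no such clause.

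**The concern.** Two analysts working from different sections would report different results for five endpoints. Section 7.9.2 uses several of these (mortality, colectomy or ileostomy, bacteremia) as safety-related outcomes. The trial is open label, so an anchor left unsettled could be chosen after the data are seen.

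Following 3.2.2 raises three problems.

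- Controls never receive FMT. They have no start date for mortality and surgery, and no end date for hospital days, ICU days and bacteremia. The same holds for a subject randomized to FMT but never dosed, who belongs in the secondary ITT analysis of Section 8.6.
- Borrowing enrollment as the control anchor leaves unequal observation time. The extra days go to FMT subjects who still meet severity criteria and are redosed.
- The hospital-days bullet does not say which dose it means, while the ICU bullet says the last. If the first dose is meant, ICU days are counted over a longer window than the hospital days that contain them.

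**Working it through.** **Side by side.** The plan gives no figure to reproduce here, so the first step is to compare the anchors.

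| Endpoint | Section 3.2.2 | Section 8.2 |
|---|---|---|
| Mortality | last FMT + 30 and + 60 d | enrollment + 30 and + 60 d |
| Colectomy/ileostomy | last FMT + 30 d | enrollment + 30 d |
| Hospital days | enrollment to FMT + 30 d (dose not named) | enrollment to enrollment + 30 d |
| ICU days | enrollment to last FMT + 30 d | enrollment to enrollment + 30 d |
| Bacteremia | enrollment to last FMT + 30 d | enrollment to enrollment + 30 d |
| Readmission | index discharge + 60 d | index discharge + 60 d |

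Five of the six differ.

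**Extra window per FMT subject.** Table 3 puts enrollment on study day 1 and doses on days 1, 4 and 7, with a one-day allowance. If the first dose is on day 2, "then the second and third administration dates (if eligible) will be days 5 and 8 (+/- 1 calendar day"). Days from enrollment to last dose:

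- One dose: day 1 or 2, so 0 to 1.
- Two doses: nominally 4 − 1 = 3. Earliest day 4 − 1 = 3, so 2; latest day 5 + 1 = 6, so 5.
- Three doses: nominally 7 − 1 = 6. Earliest day 7 − 1 = 6, so 5; latest day 8 + 1 = 9, so 8.

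The longest windows are therefore 30 + 8 = 38 days (38/30, 27% longer) and 60 + 8 = 68 days (68/60, 13% longer). If the hospital-days bullet means the first dose, that window ends at 30 + 1 = 31 days at the latest, against 38 for ICU days.

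The later anchor lengthens the time at risk for mortality and surgery rather than merely shifting it. A subject who dies after dose 1 has dose 1 as the last dose, so the death counts. Bowel surgery bars further dosing (Sections 3.2.1 and 5.2), so it counts too.

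**Arm-level size.** The share redosed is not in the plan. Assume a share q is redosed at each of the two decision points, on the nominal schedule. One, two and three doses then have probabilities 1 − q, q(1 − q) and q², and the mean extra window is 3q(1 − q) + 6q² days.

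Assume also that both arms have the same constant hazard, with 20% risk at 30 days, and that controls are counted from enrollment. Risk over 33 days is 1 − 0.8^(33/30) = 0.218, and over 36 days 1 − 0.8^(36/30) = 0.235. Weighting 0.200, 0.218 and 0.235 by the dose probabilities gives:

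| q | Mean extra days | Share of 30 d | FMT-arm risk | Spurious excess |
|---|---|---|---|---|
| 0.2 | 0.72 | 2.4% | 0.204 | 0.4 points |
| 0.5 | 2.25 | 7.5% | 0.213 | 1.3 points |
| 0.8 | 4.32 | 14.4% | 0.225 | 2.5 points |

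**Offset.** For mortality and surgery, 3.2.2 omits events between randomization and the first dose. For a one-day gap this is at most 1 − 0.8^(1/30) = 0.007, or 0.7 points. There is no such offset for hospital days, ICU days and bacteremia, which start at enrollment in both sections.

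**The case against.** The strongest reply is that Section 8.2 sits in the statistical plan and already gives a complete window, the same in every arm, for all five endpoints. Controls are anchored on enrollment throughout the follow-up sections, so an analyst would borrow that date rather than invent one. Section 8.5.2 specifies a test only for the primary outcome, so no planned secondary test or error rate is at stake. All of this is correct, and it limits the weight of the point. It does not remove the conflict: 8.2 itself sends the reader to 3.2.2 for the detail, no precedence is stated, and the borrowed anchor leaves redosed subjects with longer windows and never-dosed FMT subjects with none.

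The size can also be challenged. With exponential resolution times, redosing at day 3 treated as non-resolution, and the FMT durations of 2 and 4 days that Section 8.4 highlights, q is about 0.22 (mean 2 days: e^(−3/2)) to 0.59 (median 4 days: 2^(−3/4)). The excess is then about 0.5 to 1.7 points. One event in the 60 planned FMT subjects is 1/60 = 1.7 points, so the distortion is about one event or less. That is fair, and the 2.5-point figure is an upper scenario.

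Two smaller points stand in part. The missing word in the hospital-days bullet is probably a slip, since the other four FMT-anchored bullets name the last dose. And if the one-day interval allowances in Section 3.1 accumulate, the last dose falls 1 + 4 + 4 = 9 days after enrollment, giving 39 and 69 days. Sections 3.1.4 and 5.2 and Table 3 count from the first dose and support 38 and 68.

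**Conclusion.** The concern holds: the two sections contradict each other on five of six secondary endpoints, and the 3.2.2 version cannot be applied to controls or to never-dosed FMT subjects. It should be fixed. The effect is modest. With controls counted from enrollment, individual windows differ by up to 8 days on the Table 3 schedule, and the arm-level excess is 0.4 to 2.5 points for q from 0.2 to 0.8. Those points rest on the assumed redosing share, the 20% risk and the constant, equal hazard, none of which the plan supplies. The net direction is probably against FMT, because a longer window can only add events or days; for mortality and surgery it is partly offset by the omitted pre-dose events. The contradiction itself needs no assumption. The primary endpoint and the power table are untouched, and the problem disappears if 8.2 is followed.

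**What to change.** Rewrite Section 3.2.2 to match Section 8.2. The windows for mortality, colectomy/ileostomy, hospital days, ICU days and bacteremia should run from enrollment (or randomization, if that is the date chosen) to day 30, and also to day 60 for mortality. They should apply in every arm and to FMT-randomized subjects who are never dosed. All windows are then 30 or 60 days, and the difference between arms is zero. If a post-dose version is wanted, label it as a supplementary description within the FMT arms and name the dose it counts from.

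The cost is wording in 3.2.2. No visits are added: under Section 6.5 "each study visit is intended to retrospectively cover the time period since the last study visit", the 90-day contact falls no earlier than 90 − 7 = 83 days after enrollment in any arm, and Section 7.1 provides record review at the follow-ups. Days 0 to 60 are therefore already covered. No dosing or other clinical rule changes.

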**Figure 1: Allocation to Interventional Group Flow Diagram**

### 3.2. Study Endpoints

#### 3.2.1. Primary Study Endpoints

The primary outcome is resolution of symptoms associated with S/SC/F-CDI, listed below. The primary outcome will be satisfied when the subject is discharged from the hospital (not to hospice or palliative care) or, while the subject remains hospitalized, when the following criteria are met for 72 hours:

- If radiology study or studies performed, ileus/dilation/megacolon either not noted or noted as resolved (electronic medical record search words: “ileus”, “dilated”, “dilation”, or “megacolon”)
- Ileus/megacolon either noted as resolved by any provider documentation or not noted (electronic medical record search words: “ileus”, “megacolon”)
- WBC < 15,000 cells/uL
- Serum creatinine decreased, unchanged, or increased by  $\leq 0.2$  mg/dL over 72 hours (if not receiving continuous renal replacement therapy (CRRT) or hemodialysis (HD))
- Lactate  $\leq 2.2$  mmol/L (if measured by clinical care team)
- No vasopressors used (including epinephrine, norepinephrine, phenylephrine, or vasopressin)
- Temperature  $< 38.5$  °C and  $\geq 35.6$  °C
- < 8 bowel movements per day and < 600 mL unformed stool (if volume recorded)
- Meeting fewer than 3 systemic inflammatory response syndrome (SIRS) criteria (i.e., no more than two of the following: heart rate > 90 beats per minute; respiratory rate > 20 breaths per minute or PaCO2 < 32 mmHg; temperature > 38°C or < 36°C; WBC > 12,000 cells/uL, < 4,000 cells/uL, or > 10% immature (band) forms)

Discharge to hospice, need for bowel surgery (colectomy, diverting ileostomy), and death will count as failures. Subjects who undergo bowel surgery after initial PMT administration will not be eligible for additional administrations.

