### **8.5.2. Efficacy Analysis**

A modified intention-to-treat (m-ITT) analysis will be performed for the primary outcome of time to CDI resolution (endpoint outlined above). In the m-ITT analysis, subjects who die following randomization but before receiving their first FMT will be excluded. A competing risks survival model will be used to compare the FMT (aggregate) and no-FMT groups. A p-value (one-sided) of  $<0.2$  will be considered significant.

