## **8.6. *Subject Population(s) for Analysis***

For the primary analysis, a modified intention-to-treat (mITT) population will be used, in which subjects who die following randomization but before receiving their first FMT will be excluded. Secondary intention-to-treat and per-protocol analyses will also be performed. All randomized subjects will be included in the latter analyses.

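### Hospital-day and ICU-day counts have no rule for subjects who die in the window, so an arm that prevents early deaths can look worse

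*Combined protocol and SAP*

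**What the plan says.** Section 3.2.2 (Secondary Study Endpoints) lists two day counts: "Cumulative days of hospitalization from enrollment until 30 days after FMT" and "Cumulative days in intensive care unit from enrollment until 30 days after last FMT". Section 8.2 refers back to that list but restates it with a different end of window: "cumulative days of hospitalization from enrollment until 30 days after enrollment, cumulative days in intensive care unit from enrollment until 30 days after enrollment". Neither section says how a death inside the window is scored.

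Mortality is a separate item in the same list, "All-cause mortality at 30- and 60-days following last FMT", and is not linked to the day counts.

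Death is handled explicitly only for the primary endpoint. Section 3.2.1 says "Discharge to hospice, need for bowel surgery (colectomy, diverting ileostomy), and death will count as failures", and Section 8.5.2 says "A competing risks survival model will be used to compare the FMT (aggregate) and no-FMT groups". The modified intention-to-treat rule in Section 8.6, under which "subjects who die following randomization but before receiving their first FMT will be excluded", is written for the primary analysis. It concerns only deaths before the first dose.

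Sections 8.5.1 to 8.5.5 give no analysis method for any secondary endpoint. No measure that combines stay with survival appears anywhere in the document.

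**The concern.** A count of days in hospital stops when the subject dies. A subject who dies on day 3 contributes at most 3 days, fewer than a survivor who recovers and goes home on day 12. If one arm has fewer early deaths, it has more subjects who live long enough to accrue a full stay, and its mean count can rise for that reason alone.

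The plan's own premises make this relevant. Section 1.1 describes severe and fulminant disease as carrying a high death rate, and Section 12.2 names fewer deaths among the hoped-for benefits. So the event that cuts the count short is one the treatment may change. At stake is the interpretation of two secondary endpoints. The hospital-day comparison in particular could point against FMT when FMT is helping.

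**Working it through.** The plan states no figure for hospital or ICU days, so there is none to reproduce. The mortality, death-day and stay values below are assumptions, shown as a range.

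**Set-up.** Let p be the proportion dying in a 30-day window, d the day of in-hospital death, and L the survivors' stay in days.

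- Mean raw hospital days = p × d + (1 − p) × L
- Mean days alive and out of hospital, with days after death scored 0 = (1 − p) × (30 − L)

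With the same L and d in both arms and death rates p_C (control) and p_F (FMT):

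- Raw difference, FMT minus control = (p_C − p_F) × (L − d)
- Difference in days alive and out of hospital = (p_C − p_F) × (30 − L)

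The raw difference is positive (FMT looks worse) whenever decedents accrue fewer days than survivors. The second difference favors FMT for any L below 30.

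| L | d | Mortality, control v FMT | Raw days, control v FMT | Difference | Days alive and out of hospital, control v FMT | Difference |
|---|---|---|---|---|---|---|
| 6 | 5 | 20% v 10% | 5.8 v 5.9 | +0.1 | 19.2 v 21.6 | +2.4 |
| 12 | 4 | 20% v 10% | 10.4 v 11.2 | +0.8 | 14.4 v 16.2 | +1.8 |
| 14 | 5 | 20% v 10% | 12.2 v 13.1 | +0.9 | 12.8 v 14.4 | +1.6 |
| 14 | 5 | 30% v 15% | 11.30 v 12.65 | +1.35 | 11.2 v 13.6 | +2.4 |
| 18 | 3 | 30% v 15% | 13.5 v 15.75 | +2.25 | 8.4 v 10.2 | +1.8 |
| 6 | 10 | 20% v 10% | 6.8 v 6.4 | −0.4 | 19.2 v 21.6 | +2.4 |
| 14 | 15 | 30% v 15% | 14.3 v 14.15 | −0.15 | 11.2 v 13.6 | +2.4 |

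**Range.** For L from 6 to 18, d from 3 to 5, and mortality halved from 20% or 30%, the smallest raw difference is 0.10 × (6 − 5) = 0.1 day and the largest is 0.15 × (18 − 3) = 2.25 days, both against FMT. Over the same cases, days alive and out of hospital improve by between 0.10 × (30 − 18) = 1.2 and 0.15 × (30 − 6) = 3.6 days.

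**If rescued subjects have long stays.** Suppose each prevented death becomes a 25-day stay. The raw count then looks worse by 0.10 × (25 − 5) = 2.0 to 0.15 × (25 − 3) = 3.3 days. Days alive and out of hospital still improve, by 0.10 × 5 = 0.5 to 0.15 × 5 = 0.75 day.

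**When the sign does not reverse.** The last two table rows have deaths later than the usual survivor stay, and the raw count then favors FMT. A shorter survivor stay under FMT also offsets the effect. With L = 12, d = 4 and 20% v 10%, the break-even FMT survivor stay solves 0.9 × L′ + 0.1 × 4 = 10.4. This gives L′ = 11.1, a cut of about 0.9 day (about 7%). With L = 14 and d = 5, the cut needed is 1.0 day (20% v 10%) or 1.6 days (30% v 15%).

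**ICU days.** The same formula applies with ICU days in place of L and d, but survivors may average very few. If survivors average 1 ICU day and decedents 4, control is 0.8 × 1 + 0.2 × 4 = 1.6 and FMT is 0.9 × 1 + 0.1 × 4 = 1.3. The raw count then favors FMT. The sign reverses only if survivors average more ICU days than decedents.

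**Window.** Section 3.2.2 ends the ICU count 30 days after the last FMT. Table 3 puts retreatment on nominal days 4 and 7, so a subject given three doses has a window 7 − 1 = 6 days longer than one dosed only on day 1. Control subjects have no FMT date. Section 8.2 uses 30 days from enrollment for everyone.

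**The case against.** The strongest reply has four parts.

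- **Mortality is in the same list**, at 30 and 60 days, so a reader would see deaths beside the day counts. This helps interpretation. It does not correct the comparison of counts.
- **The effect is conditional.** It needs decedents to accrue fewer days than survivors, and it assumes FMT leaves survivor stay unchanged. The trial is planned around 25% to 75% shorter symptom duration (Section 8.4). Symptom duration is not length of stay, but a 7% shorter stay is enough to cancel the reversal in the 12-day example. This stands, and it limits the claim to what can happen.
- **ICU care is not an entry requirement.** Under Section 4.1 and Table 2, a raised white cell count or acute kidney injury alone qualifies, and Section 3.1.6 expects some subjects to be eating and taking oral medication. Many survivors may have no ICU days. This also stands, so a reversal on ICU days is not shown.
- **No decision rests on these endpoints.** The one-sided p < 0.2 criterion in Section 8.5.2 is stated for the primary outcome, where death already counts as failure.

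A reader might also infer that early death earns the best possible score. It does not: a survivor discharged on day 2 has fewer hospital days than a subject who dies on day 3, and anyone never in ICU scores 0 there. A reader might infer that the plan instructs the analyst to ignore death. It is silent, which is different.

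**Conclusion.** The gap is real and worth closing before analysis. Both day counts lack a rule for death in a population where the protocol expects deaths and hopes to reduce them. On hospital days, an arm that halves mortality can look 0.1 to 2.25 days worse, assuming survivor stays of 6 to 18 days, deaths on days 3 to 5, control mortality of 20% or 30%, and equal survivor stay in both arms. None of these inputs is given in the documents.

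The documents do not support saying that an arm that prevents deaths will look worse, or that both endpoints will have the wrong sign. The hospital-day reversal depends on when deaths occur and on whether survivor stay changes. For ICU days the bias is possible and its direction unknown. The primary conclusion is not affected.

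**What to change.** In Sections 3.2.2 and 8.2, make the analyzed endpoints days alive and out of hospital, and days alive and out of ICU, from enrollment (randomization) to day 30 in both arms, with every day after death scored 0. Report raw hospital and ICU days descriptively, next to mortality. Worst-rank scoring of deaths, or day counts reported jointly with mortality, would be acceptable alternatives. Whichever is chosen should be written down, with the analysis method, before the data are examined. State also how days in hospice are scored, because discharge to hospice shortens the hospital count in the same way and is a failure for the primary endpoint.

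Align Section 3.2.2 with the enrollment-anchored window of Section 8.2. A window ending after the last FMT is undefined for control and longer for retreated subjects.

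The cost is a wording change. Admission, discharge, ICU and death dates are already needed for the listed endpoints. The downside is that the new measure mixes survival with stay, so a difference may come mainly from deaths, and it is less direct for resource use. The descriptive table covers that need.

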### **3.1.2. Study Intervention Phase**

All S/SC/F-CDI trial interventions will be performed inpatient at the listed study site hospitals. During the intervention period, following informed consent and randomization, subjects in either the upper GI (PMT-002 or PMT-003) or lower GI (PMT-001) intervention arm will receive single-dose PMT administration, with PMT formulation and route of administration (suspension for enema, suspension for enteric delivery, or oral capsules) determined per randomization and stratification scheme ([Section 3.1.6](#)). Administration of the product will take place over 10 to 90 minutes (target 30 minutes). Subjects randomized to PMT will be eligible to receive up to two additional administrations of PMT (by clinically appropriate route of administration) at 3-day (+/- 1 day) intervals, if they fail to meet criteria for clinical improvement ([Section 3.2.1](#)). Antibiotics prescribed as part of routine clinical care for CDI will not be altered by the intervention.

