#### 7.9.2. **Safety Parameters**

Safety will be monitored in several ways:

- 30- and 60-minute observations with vital sign checks after investigational product administration.
- Follow-up daily for 3 days and at 7 days, 30 days, 90 days, and 180 days as outlined in the schedule of study procedures ([Table 3](#)).
- Examination of safety-related secondary outcomes, including: bacteremia, mortality, hospital admission, colectomy or diverting ileostomy.

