### ***12.2. Benefits***

Potential direct benefits include: cure or improvement of CDI symptoms more quickly than with standard of care, reduction in risk of complications of CDI (death, need for surgery), reduction in risk of recurrence of CDI, which have been suggested by observational studies to date (Table 1). Indirect benefits include contributing to medical knowledge about the utility of FMT in this study population and therefore helping patients who have this disease in the future.

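### Readmission is counted from index discharge with no rule for in-hospital death, so better survival on FMT can by itself raise the readmission rate

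*Combined protocol and SAP*

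**What the plan says.** Section 3.2.2 of the combined protocol and SAP lists "Repeat hospital admission within 60 days of discharge from index hospitalization". The statistical section repeats it in 8.2 as "readmission within 60 days of discharge from index hospitalization". The other endpoints in 8.2 are counted from enrollment, for example "all-cause mortality (30- and 60-days following enrollment"; readmission alone starts at a later event.

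That event follows randomization, because "All S/SC/F-CDI trial interventions will be performed inpatient at the listed study site hospitals" (Section 3.1.2). It is also an efficacy outcome. Section 3.2.1 states: "The primary outcome will be satisfied when the subject is discharged from the hospital (not to hospice or palliative care". Section 12.2 names among the hoped-for benefits a "reduction in risk of complications of CDI (death, need for surgery".

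Section 7.9.2 gives the endpoint a safety use: "Examination of safety-related secondary outcomes, including: bacteremia, mortality, hospital admission, colectomy or diverting ileostomy".

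On death and hospice, Section 3.2.1 says "Discharge to hospice, need for bowel surgery (colectomy, diverting ileostomy), and death will count as failures", but this concerns the primary outcome. The competing-risks model in Section 8.5.2 is also for the primary outcome. Section 8.6 promises secondary intention-to-treat and per-protocol analyses without linking either to readmission. No section gives a denominator for readmission or says how in-hospital death, hospice discharge or a continuing index stay is handled.

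**The concern.** The text says only discharge, but a subject who dies during the index stay cannot be readmitted. Entry to the risk set therefore requires live discharge, which FMT is meant to make more likely and earlier. Each natural denominator then has a weakness:

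- **All randomized subjects.** An in-hospital death scores as not readmitted, so the arm with more deaths can look better.
- **Subjects discharged alive.** The groups are no longer those formed by randomization. If FMT saves some subjects, they join the FMT group only.

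Timing adds to this. A relapse on a given study day counts as a readmission if the subject has gone home, but is absorbed into the index stay if the subject has not.

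The endpoint is listed as safety-related, and it is the natural check on whether discharges scored as resolution came too soon. What is at stake is a false or inflated harm signal, or a true reduction in readmission that looks smaller than it is.

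**Working it through.** The plan gives no rate, power or sample size for readmission, so there is no figure of its own to reproduce. All rates below are assumptions.

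**Notation.** mC and mF are in-hospital death on standard of care (SOC) and FMT. r is readmission in subjects who would be discharged alive on either arm. rx is readmission in the extra survivors, who are discharged alive only because of FMT. FMT is first given no effect on readmission in the common survivors.

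**Formulas**
- Per randomized subject: SOC = (1 − mC)r; FMT = (1 − mC)r + (mC − mF)rx; difference = (mC − mF)rx.
- Per discharged subject: SOC = r; FMT = [(1 − mC)r + (mC − mF)rx]/(1 − mF); difference = (mC − mF)(rx − r)/(1 − mF).

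**Example:** mC = 0.20, mF = 0.10, r = 0.30.
- rx = 0.30. Per randomized: 0.24 v 0.24 + 0.10 × 0.30 = 0.27. Per discharged: 0.30 v 0.27/0.90 = 0.30.
- rx = 0.60. Per randomized: 0.24 v 0.24 + 0.10 × 0.60 = 0.30. Per discharged: 0.30 v 0.30/0.90 = 0.333.

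**Grid:** r = 0.20, 0.30 or 0.40, with rx = r or 2r, so rx runs from 0.20 to 0.80. Differences are FMT minus SOC, in points.

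| Deaths, SOC v FMT | Per randomized | Per discharged |
|---|---|---|
| 10% v 5% | 0.05 × (0.20 to 0.80) = 1 to 4 | 0 to 0.05 × 0.40/0.95 = 2.1 |
| 15% v 10% | 1 to 4 | 0 to 0.05 × 0.40/0.90 = 2.2 |
| 20% v 10% | 0.10 × (0.20 to 0.80) = 2 to 8 | 0 to 0.10 × 0.40/0.90 = 4.4 |
| 30% v 15% | 0.15 × (0.20 to 0.80) = 3 to 12 | 0 to 0.15 × 0.40/0.85 = 7.1 |

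The per-discharged difference is exactly zero in the half of the scenarios with rx = r.

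**Can the sign of a true effect reverse among discharged subjects?** The grid cannot show this, because it contains no true readmission effect. Let FMT multiply readmission in the common survivors by k < 1. The discharged FMT rate exceeds r only if

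rx > r[(1 − mF) − (1 − mC)k]/(mC − mF).

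With r = 0.30, deaths 20% v 10% and k = 0.9, this is 0.30 × (0.90 − 0.72)/0.10 = 0.54. The thresholds are:

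| Deaths, SOC v FMT | k = 0.9 | k = 0.8 |
|---|---|---|
| 10% v 5% | 84% | not attainable (138%) |
| 20% v 10% | 54% | 78% |
| 30% v 15% | 44% | 58% |
| 40% v 20% | 39% | 48% |

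Below the threshold the benefit keeps its sign. If rx lies between kr and the threshold, the benefit looks smaller than it is.

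The all-randomized count is more easily moved, because every extra survivor adds to it. With deaths 20% v 10%, k = 0.9 and r = rx = 0.30, it gives 24.0% v 0.80 × 0.27 + 0.10 × 0.30 = 24.6%. That excess comes from survival, since FMT lowers readmission in the common survivors.

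**The case against.** **The plan names no test and no denominator.** A reader might infer that it sets out to compare arms in non-randomized groups. No section says so. The supportable complaint is that the denominator and the handling of death are missing, and that neither obvious way of filling the gap is safe if FMT changes survival or discharge. This part of the objection stands.

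**Sign reversal is not established.** A reader might infer that readmission will point the wrong way. Among discharged subjects that needs a large excess of readmission in the extra survivors, and the documents do not say that they would be sicker. Nor does a composite of readmission or death that favors FMT throughout the grid prove anything. Its difference is (mC − mF)(1 − rx), which is positive whenever FMT lowers death and rx < 1, and every death pair was chosen that way. This also stands.

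**The distortion is small beside sampling error.** With 2:1 allocation of 90 subjects (30 v 60), the example gives 24 v 54 discharged alive. The standard error of 30% v 33.3% is √(0.30 × 0.70/24 + 0.333 × 0.667/54) ≈ 0.113, or 11 points, against a gap of about 3. This is true, but the bias has a known cause and can be removed cheaply.

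**Other reporting covers part of the gap.** Mortality is its own endpoint and stands beside hospital admission in Section 7.9.2. SAEs, which include events that require or prolong a hospital stay (Section 9.1.2), are a primary safety endpoint (Section 3.2.3), with adverse events collected from enrollment in all randomized subjects (Section 8.5.4). This softens the harm. It does not make the readmission figure itself interpretable.

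**A discharge-started clock suits a check on premature discharge.** It does, which is a reason to keep that figure as a description.

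**Conclusion.** The concern holds in a limited form. Readmission starts at an event after randomization that itself scores as primary success, only subjects discharged alive can have it, and no rule covers in-hospital death. If FMT lowers in-hospital death, readmission per randomized subject rises by 1 to 12 points through survival alone over the assumed range. Among discharged subjects the distortion is 0 to 7 points, and it vanishes if the extra survivors are readmitted at the common rate. Among discharged subjects, a true benefit changes sign only if extra survivors are readmitted much more often, for example above 54% with deaths of 20% v 10%, a common rate of 30% and a true 10% relative reduction.

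All of this rests on assumed rates and on FMT lowering in-hospital death. The documents call mortality high in this disease (Section 1.1) but give no figure. The primary conclusion is untouched. The change is worth making because the endpoint has a stated safety use and the data are already being collected.

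**What to change.** In Sections 3.2.2 and 8.2:

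1. Compare arms in all randomized subjects on death or readmission by a fixed day from enrollment, within existing follow-up. Day 60 would match the mortality endpoint in 8.2. Show deaths and readmissions separately by arm.
2. Add days alive and out of hospital from enrollment to the same day. The composite alone still gives subjects discharged earlier more time in which to be readmitted. With this measure, hospital days from a given relapse date count alike whether the subject was home or still in hospital.
3. Keep readmission within 60 days of discharge, among subjects discharged alive, as a descriptive figure shown beside mortality.

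The cost is some wording and a little more analysis. Record review at 30, 90 and 180 days (Section 7.1) already serves the secondary outcomes. The drawback is that a composite mixes two outcomes of unequal weight, which is why the components are shown.
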